5.1 Patient Evaluation Flowsheet: Pre-study (Baseline) and Post-randomization Follow-up
For Patients Randomized to Best Supportive Care (Arm 1)

| Required Investigations | PRE-STUDY (≤ 14 days prior to randomization, unless otherwise indicated) | PRIOR to objective disease progression (timing from randomization) | | AFTER objective disease progression (timing from randomization) |
|---|---|---|--|--|
| | | Every 4 weeks until objective disease progression | Every 8 weeks until objective disease progression (maintain schedule even if clinic visits are delayed) ³ | Every 12 weeks |
| History and Physical Exam | | | | |
| Including: height (baseline only), weight, ECOG performance status, clinical tumour measurements (if applicable) | X | X | | |
| Vital Signs (blood pressure, heart rate, temperature) | X | X | | |
| Concomitant Medications | X | X | | |
| Overall Survival | | | | |
| Survival Status Assessment | | X | X | X ¹ |
| Hematology | | | | |
| CBC, differential (including lymphocytes), platelets | X | X | | |
| Coagulation | | | | |
| PTT, PT/INR | X | X | | |
| Biochemistry | | | | |
| Serum Creatinine, Chloride, Sodium, Potassium, Calcium, Magnesium, Bilirubin, ALP, AST and ALT, LDH, Albumin, TSH ² , Amylase, Lipase, Serum CEA | X | X | | |
| Creatinine Clearance (calculated) | X | as clinically indicated | | |
| Glucose | X | as clinically indicated | | |
| Radiology³ | | | | |
| Chest/abdomen/pelvis CT or MRI scan ³ | X ≤ 28 days | | X ³ | |
| Other scans as necessary to document all measurable and non-measurable disease ³ | X ≤ 28 days | | | |
| Other Investigations | | | | |
| Pregnancy Test ⁴ | X | | | |
| ECG | X | as clinically indicated | | |
| Dipstick Urinalysis (including protein, specific gravity, glucose and blood) | X | | | |

table continued on next page ...

| Correlative Studies | | | |
|--|--|---|--|
| Archival Tissue Sample ⁵ (mandatory) | Availability of sufficient tissue must be confirmed prior to randomization | Submit tissue within 4 weeks of randomization | |
| Whole blood, plasma and serum ^{5,6} (mandatory) | X | To be done at 8 weeks, and at the time of objective disease progression ⁷ , if not already done | |
| Adverse Events | | | |
| Adverse Event Assessment ⁸ | X (To document residual adverse events from previous therapy and baseline symptoms) | X To be evaluated continuously for adverse events (until objective disease progression) | |
| Quality of Life | | | |

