13.0 STATISTICAL CONSIDERATIONS

13.1 Objectives and Design

The primary objective of this phase II randomized study is to assess the effect of the combination of durvalumab and tremelimumab and best supportive care (BSC) on the Overall Survival of patients with refractory, advanced colorectal cancer. Patients will be randomized to receive either combination of durvalumab and tremelimumab plus best supportive care, or best supportive care only in a 2:1 ratio after stratification by ECOG performance status (0 versus 1). Secondary objectives include comparisons of Progression Free Survival, Objective Response Rate, and Adverse Events between the two treatment arms.

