Progression-Free Survival (PFS) is defined as the time from randomization to the first objective documentation of disease progression or death due to any cause. If a patient has not progressed or died at the time of final analysis, PFS will be censored on the date of the last tumour assessment. This includes patients who are lost to follow-up or have withdrawn consent. All analyses for OS will also be performed for PFS, using similar methodology. A sensitivity analysis of PFS will also be performed where PFS is defined as the time from randomization to the second documentation of unequivocal disease progression in those patients who continued study therapy beyond the first objective documentation of disease progression and with interim CR, PR or SD documented.

Objective Response Rate:

Objective Response Rate (ORR) is defined as the proportion of patients with a documented complete response and partial response based on RECIST 1.1. The primary estimate of ORR will be based on all patients randomized. A Cochran-Mantel-Haenszel test adjusting for the stratification factors (ECOG performance status, site of tumour) at the time of randomization will be used to compare the objective response rates between two arms. A sensitivity analysis of ORR will also be performed where response is defined as the proportion of patients with a documented complete response and partial response based on RECIST 1.1 and/or Immune-Related Response Criteria (irRC) [Wolchok 2009].

Safety Analysis:

All patients who have received at least one dose of protocol treatment will be included in the safety analysis. The incidence of adverse events will be summarized by type of adverse event and severity using the NCI Common Terminology Criteria for Adverse Events. A Fisher's exact test will be used to compare adverse events between the two arms if required.

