APPENDIX IV - DOCUMENTATION FOR STUDY

Follow-up is required for patients from the time of randomization and will apply to all eligible patients.

This trial will use a web-based Electronic Data Capture (EDC) system for all data collection. For details of accessing the EDC system and completing the on-line Case Report Forms please refer to the “CCTG EDC Generic Data Management Guidebook” posted on the CO.26 area of the CCTG web-site (www.ctg.queensu.ca).

The electronic CRFs to be used in this trial, through the EDC system, are as follows:

| Electronic Folder | Timing | To be completed electronically | Supporting Documentation Required ¹ |
|---|--|--|--|
| Eligibility Checklist | | At the time of randomization | 
 • consent form² |
| Baseline Report | | Within 2 weeks of randomization | 
 • relevant pathology report(s) • RAS reports • relevant operative report(s) • relevant radiology reports (including CT/MRI abdomen/pelvis, CT/MRI chest, chest x-ray) • tumour measurement worksheet • ECG report |
| Correlative Studies Report (Tumour and Blood) | Continuous running-log folder See Section 5.0 | Information pertaining to tumour tissue submission must be completed as soon as possible after randomization, and tissue submitted within 4 weeks of randomization. | 
 • Consent form² • Diagnostic pathology report (for tumour tissue only) |
| | | Information pertaining to baseline/pretreatment blood collection for correlative studies (i.e. whole blood, plasma, serum) must be completed within 2 weeks of randomization. | |
| | | Information pertaining to post randomization blood collection samples (i.e. whole blood, plasma, serum) for correlative studies and banking should be completed within 2 weeks after collection of blood specimens. | |
| Concomitant Medication Report | Continuous running-log folder | | |
| Best Supportive Care Report (Arm 1 only) | Every 4 weeks (28 days) until objective progression | Within 2 weeks of the end of each reporting period | 
 • If available/applicable: • CT/MRI abdomen/pelvis report • CT/MRI chest • other radiology reports • tumour measurement worksheet • ECG report |

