| Treatment Report (Arm 2 only) | Every 4 weeks (28 days) while patient is on protocol treatment | Within 2 weeks of the end of each 4 week reporting period | If available/applicable: 
 • CT/MRI abdomen/pelvis report • CT/MRI chest • other radiology reports • tumour measurement worksheet • ECG report |

table continues on next page ...

| Electronic Folder | Timing | To be completed electronically | Supporting Documentation Required ¹ |
|--|---|---|--|
| End of Treatment Report(Arm 2 only) | As soon as permanent off treatment status is confirmed. | Within 2 weeks of end of treatment | |
| 4-Week Post-Treatment Follow-Up Report (Arm 2 only) | 4 weeks from the date of last infusion | Within 2 weeks of the 4-week post treatment follow up visit | 
 • relevant radiology reports |
| Follow-up Report ³ (Arm 2 only) | Every 4 weeks (28 days) until objective progression | Within 2 weeks of follow-up visit | If available/applicable: 
 • CT/MRI abdomen/pelvis report • tumour measurement worksheet • CT/MRI chest report • other radiology reports • ECG report |
| Short Follow-up Report | Every 12 weeks after objective disease progression | Within 2 weeks of follow-up visit | |
| Relapse/Progression Report | Upon the patient's objective disease progression / relapse | Within 4 weeks of confirmation | 
 • relevant radiology, operative and pathology reports |
| Death Report | Upon patient's death | Within 4 weeks of patient death | 
 • autopsy/post-mortem report, if performed |
| Serious Adverse Event (SAE) Report ⁴ | Within 24 hours of event At time of event and reported to CCTG | Within 1 working day ⁴ | |
| Minimal Follow-up Report ⁵ | Annual | Within 6 weeks of contact | If available/applicable: 
 • autopsy report • CT/MRI report |

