3.2 Secondary

Secondary objectives are to:

- Compare progression-free survival (PFS) between the two treatment arms.
- Compare objective response rates (ORR) between the two treatment arms.
- Assess the toxicity and safety profile of the combination of durvalumab and tremelimumab and best supportive care.

4. Endpoints

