7.7.1 Adverse Events

Adverse events will be recorded on the CCTG toxicity/adverse event-intercurrent illness case report form. Events reported on Treatment Report or 4-Week Post-Treatment Follow-Up Report for patients on the Durva+Treme arm will be defined as adverse events on Durva+Treme; Events reported on any case report forms except Form 1 will be summarized separately for patients on both arms as overall adverse events during the (whole) study.

Drug related adverse events are those events with a relation to protocol therapy of 3=possible, 4=probable or 5=definite.

Severe adverse events are those events reported with a CTCAE Grade of 3 or higher.

Comparisons between treatment arms on overall adverse events (any vs. other, severe vs. other) will be carried out using a two sided Fisher's exact test at an alpha level of two-sided 10%.

The following variables are summarized. Tabulations of overall adverse events will be presented by treatment group.

- Adverse events on Durva+Treme: worst CTCAE grade per patient (**Table 42**)
- Severe adverse events on Durva+Treme: worst CTCAE grade per patient (**Table 43**)
- Drug related adverse events on Durva+Treme: worst CTCAE grade per patient (**Table 44**)
- Overall adverse events: worst CTCAE grade per patient (**Table 45**)
- Severe overall adverse events: worst CTCAE grade per patient (**Table 46**)

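### The between-arm adverse event test in SAP 7.7.1 makes no allowance for observation time, although adverse event collection ends at progression on BSC and follows dosing on the combination arm

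*SAP*

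**What the plan says.** SAP 7.7.1 defines the pooled set: "Events reported on any case report forms except Form 1 will be summarized separately for patients on both arms as overall adverse events", over the whole study. It then states: "Comparisons between treatment arms on overall adverse events (any vs. other, severe vs. other) will be carried out" with a two-sided Fisher's exact test at 10%. Severe means CTCAE grade 3 or higher. No window, person-time or censoring rule is given.

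The protocol lists the comparison in Section 13.1: "Secondary objectives include comparisons of Progression Free Survival, Objective Response Rate, and Adverse Events between the two treatment arms". Section 13.2 is softer: "A Fisher's exact test will be used to compare adverse events between the two arms if required". SAP 3.2 asks only for a profile: "Assess the toxicity and safety profile of the combination of durvalumab and tremelimumab and best supportive care".

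Collection differs by arm.

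- **BSC (Arm 1).** The Section 5.1 flowsheet entry reads "To be evaluated continuously for adverse events (until objective disease progression", and in Appendix IV the Best Supportive Care Report is due "Every 4 weeks (28 days) until objective progression".
- **Combination (Arm 2).** The Treatment Report is due "Every 4 weeks (28 days) while patient is on protocol treatment". Sections 7.1.7 and 8.2 let dosing continue past a first RECIST progression until repeat imaging. A post-treatment visit follows: 4 weeks after the end of the last cycle in Section 5.2, but 4 weeks from the last infusion in Appendix IV. After that visit, footnote 13 of Section 5.2 speaks of events felt related to study therapy. Appendix IV also has a 4-weekly Follow-up Report for Arm 2, running to objective progression.

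**The concern.** An ever/never proportion rises with the time a patient is watched. If one arm is watched longer, a Fisher test on that proportion mixes toxicity with collection time. Here the BSC clock stops at objective progression, while the Arm 2 clock is set by dosing plus a follow-up visit. A significant severe-AE p-value favouring BSC could then arise with no difference in underlying event rates.

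The planned output would not let a reader correct for this. Treatment duration is tabulated for Arm 2 only (SAP Table 25), and no AE observation time is tabulated for BSC. For comparison, SAP 7.8 does state arm-specific reporting windows for concomitant medication. The stake is how a secondary safety comparison is read.

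**Working it through.** Neither document states an AE rate, a PFS assumption or a power for this test, so there is no plan figure to reproduce. The size below is illustrative.

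**Step 1: windows side by side.** The last infusion is on day 1 of a 28-day cycle. If dosing stops at a scan at the end of that cycle, 4 weeks from the infusion falls on the scan, and 4 weeks from the cycle end falls 4 weeks later.

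| Arm 2 patient | BSC window | Arm 2, Section 5.2 timing | Arm 2, Appendix IV timing |
|---|---|---|---|
| Stops at detected progression | to progression | + 4 weeks | + 0 |
| Dosed 4–8 weeks past progression | to progression | + 8–12 weeks | + 4–8 weeks |
| Stops after cycle 1; later forms carry related AEs only | to progression | to week 8 | to week 4 |
| Stops early; Follow-up Report carries all-cause AEs | to progression | to progression | to progression |

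**Step 2: inputs.** From the documents: 120 vs 60 patients (SAP 2.1), 8-week scans (Sections 5.1 and 5.2), Fisher at two-sided 10%, and median survival 4.5 months (Section 13.3), applied to both arms. Assumed: the same constant severe-AE hazard λ of 0.1–0.2 per month in both arms, exponential progression with median m of 1.5–2.5 months, independent exponential death, and 0–60% of Arm 2 dosed 4–8 weeks past progression.

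**Step 3: formula.** Let μ = ln 2/4.5 = 0.1540, ν = ln 2/m, τ = 8 weeks = 56/30.4375 = 1.840 months, s = λ + μ, q = exp(−ντ) and z = exp(−sτ). Then

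- BSC: p = (λ/s)(1 − L), with L = (1 − q)z/(1 − qz)
- Arm 2 with extra time δ: replace L by L·exp(−sδ).

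Example, λ = 0.2 and m = 1.9:

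- s = 0.3540, λ/s = 0.5649, q = 0.5111, z = 0.5213, so L = 0.4889 × 0.5213/(1 − 0.5111 × 0.5213) = 0.3475.
- BSC: 0.5649 × 0.6525 = 36.9%.
- Arm 2, + 4 weeks: 0.5649 × (1 − 0.3475 × 0.7220) = 42.3%.
- Arm 2, + 12 weeks: 0.5649 × (1 − 0.3475 × 0.7220 × 0.5213) = 49.1%.
- With 30% dosed 8 weeks past progression: 0.7 × 42.3 + 0.3 × 49.1 = 44.4%.

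Summing the two binomials, Bin(120, 0.444) and Bin(60, 0.369), over all tables with Fisher p ≤ 0.10 gives 21.4% rejection, of which 21.1 points lie toward more AEs on Arm 2.

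**Step 4: rejection over the assumed range, no early stopping, equal hazards.** With equal windows the test rejects in 8.0–8.5%.

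| Share dosed past progression | By | Section 5.2 timing | Appendix IV timing |
|---|---|---|---|
| 0% | – | 11.7–16.8% | 8.0–8.5% |
| 30% | 4 weeks | 13.5–21.0% | 8.4–9.0% |
| 30% | 8 weeks | 15.1–24.5% | 9.3–10.4% |
| 60% | 4 weeks | 15.6–26.0% | 9.6–11.2% |
| 60% | 8 weeks | 19.5–34.3% | 12.3–17.4% |

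In the Section 5.2 column at most 1.4 points lie in the opposite direction.

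**Step 5: the conditional reversed case.** Suppose 30% of Arm 2 stops after cycle 1, none is dosed past progression, and Appendix IV timing applies. If later forms carry related AEs only, the example becomes 0.7 × 36.9 + 0.3 × 0.5649 × (1 − 0.7220) × 100 = 30.5% vs 36.9%. Rejection over the range is 14.2–23.1%, nearly all toward fewer AEs on Arm 2. If the Follow-up Report carries all-cause AEs to progression, the windows match and rejection returns to 8.0–8.5%.

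**Step 6: any AE.** In the Step 3 model (Section 5.2 timing, m = 1.9, no early stopping), rejection is 15–19% when BSC incidence is 80% and 9–10% at 90%, with no effect from 95%. If instead every Arm 2 window were 1.5 times the BSC one, 95% on BSC becomes 1 − 0.05^1.5 = 98.9% on Arm 2, and the test rejects in 37%. The attenuation near saturation therefore depends on the model.

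**The case against.** Ever/never incidence is a usual safety summary. The stated safety objective is the profile of the combination, Section 13.2 makes the test conditional, SAP Tables 42–44 report on-treatment and drug-related events separately, and no stated decision rests on this p-value. All of that stands and limits the severity. It does not remove the point: SAP 7.7.1 prespecifies the test without condition, and Section 13.1 lists the comparison.

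The inflation is also modest in several scenarios. Under Appendix IV timing with none dosed past progression there is none. Patients dosed past progression must be clinically stable (Section 8.2) and may have fewer events: if that 30% has half the average hazard in both arms, Section 5.2 timing at m = 1.9 gives 15–19%. This stands too, and is why only a range is given.

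A reader might infer that the bias can equally run the other way, so that the test could hide added toxicity because Arm 2 patients who stop early are watched for less time. The documents do not establish this. It needs footnote 13 to restrict later collection to related events and the Arm 2 Follow-up Report to carry no all-cause AEs. That form's AE content is not shown. SAP 7.8 takes major medical problems, defined as unrelated to treatment, from the same form. This shows that unrelated problems are recorded after drug stops, but not that AEs are. The content of the Short Follow-up Report, used in both arms after progression, is likewise not shown. If it records AEs, the BSC window is longer than assumed here.

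**Conclusion.** The point holds as a low-to-moderate limitation of a secondary safety comparison; the overall survival analysis is unaffected. SAP 7.7.1 tests severe AEs over unequal collection windows with no time adjustment, and Arm 2's window is longer for patients dosed past progression. Under the assumptions in Step 2 with no early stopping, false rejection is 12–34% with Section 5.2 timing, nearly all toward more AEs on Arm 2, and 8–17% with Appendix IV timing. These are scenario figures; the upper ends need 60% of patients dosed a full 8 weeks past progression.

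A reversed bias (14–23% with 30% stopping early) arises only on the related-events-only reading and should be reported as conditional. For any AE the effect shrinks near saturation, by an amount that depends on the model.

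**What to change.** 1. Base the between-arm severe-AE test on time to first grade 3+ event, by a log-rank test at two-sided 10%, grouped by 4-week reporting period. No passage shows that AE onset dates are recorded, but the 4-weekly reports in both arms supply the period.
2. Censor each patient at the end of all-cause AE collection: objective progression on BSC; on Arm 2 the last form that records all-cause AEs (the Follow-up Report if it does, otherwise the post-treatment report); or death. State in the SAP which forms carry all-cause AEs.
3. Keep the whole-study ever/never tables descriptive, with a footnote on the unequal windows.
4. Separately, reconcile the post-treatment report timing in Section 5.2 and Appendix IV. That report also defines the on-treatment AE tables.

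The cost is SAP wording and one derivation from existing forms. In simulation at m = 1.9, censoring Arm 2 at the post-treatment report, the log-rank test rejected in 9–11% under both visit timings, balanced in direction. Other medians were not simulated. The downside is that censoring is assumed non-informative. If the AE hazard doubles after progression (Section 5.2 timing, 30% dosed past), total rejection stays at 10–11%, but 7–8 points of it lie toward more AEs on Arm 2. Related events after all-cause collection ends would appear only in the descriptive tables.

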7.7.2 Laboratory Evaluations

For patients on Durva+Treme, laboratory evaluations reported on Treatment Report or 4-Week Post-Treatment Follow-Up Report for patients on the Durva+Treme arm will be included in the calculation for laboratory adverse events on Durva+Treme. All laboratory evaluations reported after baseline assessment will be included in the calculation for overall laboratory adverse events. Laboratory results will be classified according to CTCAE version 4.0. Laboratory tests that are not covered by the CTCAE grading system will be summarized according to the following categories: normal and above the upper normal limits.

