7.7 Safety

The safety analyses will be based on the All Treated population defined in Section 6. Adverse events and laboratories are graded and categorized using the CTCAE v4.0 criteria except where CTCAE grades are not available.

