7.6.2.1 Hematology

- Hemoglobin, platelets, WBC, neutrophils, RBC, lymphocytes, monocytes, eosinophils, basophils on Durva+Treme: worst CTC grade per patient (**Table 47**)
- Overall hemoglobin, platelets, WBC, neutrophils, RBC, lymphocytes, monocytes, eosinophils, basophils: worst CTC grade per patient (**Table 48**)

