7.6.2.2 Serum Chemistry

- Total bilirubin, AST, ALT, alkaline phosphatase, LDH, serum creatinine, chloride, sodium, albumin, potassium, calcium, magnesium, ALP, amylase, lipase, CEA on Durva+Treme: worst CTC grade per patient (**Table 49**)
- Overall total bilirubin, AST, ALT, alkaline phosphatase, LDH, serum creatinine, chloride, sodium, albumin, potassium, calcium, magnesium, ALP, amylase, lipase, CEA: worst CTC grade per patient (**Table 50**)

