Event 3	** (**)	** (**)	** (**)	** (**)	** (**)	** (**)
...	** (**)	** (**)	** (**)	** (**)	** (**)	** (**)
Body System 2 ⁽¹⁾	** (**)	** (**)	** (**)	** (**)	** (**)	** (**)
Event 1	** (**)	** (**)	** (**)	** (**)	** (**)	** (**)
...	** (**)	** (**)	** (**)	** (**)	** (**)	** (**)

⁽¹⁾ Patients may have more than one event within a body system

NOTE: Same table to be made for BSC Arm

Table 15: Baseline Hematology

Data set: All Randomized Patients			
	Number of Patients (%)		
	DURVA+TREME N = ***	BSC N = ***	Total N=***
Hemoglobin			
Grade 0	** (**)	** (**)	** (**)
Grade 1	** (**)	** (**)	** (**)
Grade 2	** (**)	** (**)	** (**)
Not reported ⁽¹⁾	** (**)	** (**)	** (**)
Platelets			
Grade 0	** (**)	** (**)	** (**)
Grade 1	** (**)	** (**)	** (**)
Not reported ⁽¹⁾	** (**)	** (**)	** (**)
WBC			
Grade 0	** (**)	** (**)	** (**)
Grade 1	** (**)	** (**)	** (**)
Grade 2	** (**)	** (**)	** (**)
Grade 3	** (**)	** (**)	** (**)
Grade 4	** (**)	** (**)	** (**)
Not reported ⁽¹⁾	** (**)	** (**)	** (**)
Neutrophils			
Grade 0	** (**)	** (**)	** (**)
Grade 1	** (**)	** (**)	** (**)
Not reported ⁽¹⁾	** (**)	** (**)	** (**)
Lymphocytes			
Grade 0	** (**)	** (**)	** (**)
Grade 1	** (**)	** (**)	** (**)
Grade 2	** (**)	** (**)	** (**)
Grade 3	** (**)	** (**)	** (**)
Grade 4	** (**)	** (**)	** (**)
Not reported ⁽¹⁾	** (**)	** (**)	** (**)
RBC			
Normal	** (**)	** (**)	** (**)
High ⁽²⁾	** (**)	** (**)	** (**)
Not reported ⁽¹⁾	** (**)	** (**)	** (**)
Monocytes			
Normal	** (**)	** (**)	** (**)
High ⁽²⁾	** (**)	** (**)	** (**)
Not reported ⁽¹⁾	** (**)	** (**)	** (**)
Eosinophils			
Normal	** (**)	** (**)	** (**)
High ⁽²⁾	** (**)	** (**)	** (**)
Not reported ⁽¹⁾	** (**)	** (**)	** (**)
Basophils			
Normal	** (**)	** (**)	** (**)
High ⁽²⁾	** (**)	** (**)	** (**)
Not reported ⁽¹⁾	** (**)	** (**)	** (**)

⁽¹⁾ Not done or outside the 14-day window prior to start of therapy

⁽²⁾ High than upper lower limit

Table 16: Baseline Chemistry

Data set: All Randomized Patients			
	Number of Patients (%)		
	DURVA+TREME N = ***	BSC N = ***	Total N=***
Total bilirubin			
Grade 0	** (**)	** (**)	** (**)
Grade 1	** (**)	** (**)	** (**)
Grade 2	** (**)	** (**)	** (**)
Not reported ⁽¹⁾	** (**)	** (**)	** (**)
Alkaline phosphatase			
Grade 0	** (**)	** (**)	** (**)
Grade 1	** (**)	** (**)	** (**)
Grade 2	** (**)	** (**)	** (**)
Grade 3	** (**)	** (**)	** (**)
Grade 4	** (**)	** (**)	** (**)
Not reported ⁽¹⁾	** (**)	** (**)	** (**)
ALT			
Grade 0	** (**)	** (**)	** (**)

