	DURVA+TREME			BSC		
	N=***			N=***		
	Worse Grade					
	Grade 3	Grade 4	Grade 5	Grade 3	Grade 4	Grade 5
Patients with any severe AE	** (**)	** (**)	** (**)	** (**)	** (**)	** (**)
Patients with severe AE within category:						
Category 1 ⁽¹⁾						
Event 1	** (**)	** (**)	** (**)	** (**)	** (**)	** (**)
Event 2	** (**)	** (**)	** (**)	** (**)	** (**)	** (**)
Event 3	** (**)	** (**)	** (**)	** (**)	** (**)	** (**)
...						
Category 2 ⁽¹⁾						
Event 1	** (**)	** (**)	** (**)	** (**)	** (**)	** (**)
...						

(1) Patients may have more than one event within a category.

Table 47: Hematology during Durvalumab and Tremelimumab Treatment

Data set: All Treated Patients on DURVA+TREME Arm	
	Number of Patients (%)
	DURVA+TREME N = ***
Hemoglobin	
Grade 1	** (**)
Grade 2	** (**)
Grade 3	** (**)
Grade 4	** (**)
Platelet	
Grade 1	** (**)
Grade 2	** (**)
Grade 3	** (**)
Grade 4	** (**)
WBC	
Grade 1	** (**)
Grade 2	** (**)
Grade 3	** (**)
Grade 4	** (**)
Neutrophils	
Grade 1	** (**)
Grade 2	** (**)
Grade 3	** (**)
Grade 4	** (**)
RBC	
Normal	** (**)
High ⁽¹⁾	** (**)
Lymphocytes	
Grade 1	** (**)
Grade 2	** (**)
Grade 3	** (**)
Grade 4	** (**)
Monocytes	
Normal	** (**)
High ⁽¹⁾	** (**)
Eosinophils	
Normal	** (**)
High ⁽¹⁾	** (**)
Basophils	
Normal	** (**)
High ⁽¹⁾	** (**)

⁽¹⁾ Greater than upper normal limit

Table 48: Overall Hematology: Worst Grade per Patient

Data set: All Treated Patients		
	Number of Patients (%)	
	DURVA+TREME N = ***	BSC N = ***
Hemoglobin		
Grade 1	** (**)	** (**)
Grade 2	** (**)	** (**)
Grade 3	** (**)	** (**)
Grade 4	** (**)	** (**)
Platelet		
Grade 1	** (**)	** (**)
Grade 2	** (**)	** (**)
Grade 3	** (**)	** (**)
Grade 4	** (**)	** (**)
WBC		
Grade 1	** (**)	** (**)
Grade 2	** (**)	** (**)
Grade 3	** (**)	** (**)
Grade 4	** (**)	** (**)
Neutrophils		
Grade 1	** (**)	** (**)
Grade 2	** (**)	** (**)
Grade 3	** (**)	** (**)
Grade 4	** (**)	** (**)
RBC		
Normal	** (**)	** (**)
High ⁽¹⁾	** (**)	** (**)
Lymphocytes		
Grade 1	** (**)	** (**)
Grade 2	** (**)	** (**)
Grade 3	** (**)	** (**)
Grade 4	** (**)	** (**)
Monocytes		
Normal	** (**)	** (**)
High ⁽¹⁾	** (**)	** (**)
Eosinophils		
Normal	** (**)	** (**)
High ⁽¹⁾	** (**)	** (**)
Basophils		
Normal	** (**)	** (**)
High ⁽¹⁾	** (**)	** (**)

⁽¹⁾ Greater than upper normal limit

**Table 49: Serum Chemistry during Durvalumab and Tremelimumab
Treatment: Worst Grade per Patient**

Data set: All Treated Patients on DURVA+TREME Arm	
	Number of Patients (%)
	DURVA+TREME N = ***
Total bilirubin	

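### Laboratory tests without a CTCAE grade have no row for low values, and the thyroid shells break the same rule by having no row for high ones

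*SAP*

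**What the plan says.** SAP 7.7 states that laboratory results are "graded and categorized using the CTCAE v4.0 criteria except where CTCAE grades are not available". For the remainder, 7.7.2 gives the rule: these tests are "summarized according to the following categories: normal and above the upper normal limits".

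The shells in Appendix 1 put this into rows. RBC, monocytes, eosinophils and basophils each have Normal and High in Tables 15, 47 and 48. Chloride, LDH and CEA have the same two rows in Tables 16, 49 and 50. In Tables 47 to 50 a footnote defines High as "Greater than upper normal limit". The baseline shells (15 and 16) add a row for results not reported, which a footnote limits to "Not done or outside the 14-day window prior to start of therapy".

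The list of hematology variables reads "Hemoglobin, platelets, WBC, neutrophils, RBC, lymphocytes, monocytes, eosinophils, basophils on Durva+Treme: worst CTC grade per patient", and the chemistry list, which includes chloride, also ends in worst grade per patient. The shells do not grade RBC or chloride, so for these two tests the 7.7.2 rule is the one that operates.

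**The concern.** Each of the five tests can be abnormal in either direction, and the rule names only one. For RBC the unnamed direction is the expected one. Protocol 4.1.21 sets the hemoglobin floor at 90 g/L, and Table 15 itself provides baseline rows for hemoglobin Grades 1 and 2, so the authors expected some anemic patients. The same table could show graded anemia and, a few rows down, no low red cell counts at all.

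The adverse event tables are not a dependable backstop. Protocol 9.1.2 says that, on the durvalumab and tremelimumab arm, laboratory abnormalities for protocol-specified tests are derived from the submitted values and are not recorded as adverse events. The blood count with differential and chloride are scheduled tests in both arms (Protocol 5.1 and 5.2). A low chloride would normally be visible only in the laboratory tables, where it has no row.

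At stake is the completeness of the laboratory safety summary, not any efficacy result.

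**Working it through.** No arithmetic in the plan bears on this point, so the check sets the 7.7.2 rule against the rows of each shell.

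| Tests | Shells | Rows for a measured value | Row absent |
|---|---|---|---|
| RBC, monocytes, eosinophils, basophils | 15, 47, 48 | Normal, High | below lower limit |
| Chloride | 16, 49, 50 | Normal, High | below lower limit |
| LDH, CEA | 16, 49, 50 | Normal, High | below lower limit |
| TSH, free T3, total T3, free T4, total T4 | 17, 51, 52 | Normal, three bands below lower limit | above upper limit |
| Sodium, potassium, calcium, magnesium, albumin | 16, 49, 50 | graded separately as hyper- and hypo- | none |

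1. *Low rows missing.* Four hematology tests in three shells and chloride in three shells give 4 × 3 + 1 × 3 = 15 places where a low value has no row. LDH and CEA are left out of this count as a judgement: only the high side is informative for them here.

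2. *Where a low value could go.* High excludes it by definition. The not-reported row in Tables 15 and 16 excludes it too, because the test was done and in window. That leaves Normal, or omission from the table.

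3. *Which of the two.* The SAP is silent. In Tables 47 to 50 the graded tests list Grades 1 to 4 with no Grade 0 and no row for missing results, so those shells do not place every patient in a row. Omission is therefore as consistent with the text as counting as Normal.

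4. *Whether leaving out low values is a consistent policy.* It is not. Five electrolyte and protein tests have separate hypo- rows, and the thyroid shells have bands below the lower limit.

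5. *The thyroid shells against the rule.* They are ungraded, so 7.7.2 as written gives them Normal and above the upper limit. They have the reverse: 5 × 3 = 15 places with no high row. Protocol 9.1.1 lists both hyperthyroidism and hypothyroidism as events of special interest, and Protocol Appendix III gives guidance on raised TSH, so this gap bears more directly on the trial than low basophils do.

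6. *Scope.* Tables 15 and 16 are baseline tables under SAP 7.4.6 that use the same row pattern. Tables 47 and 49 cover the durvalumab and tremelimumab arm only. Tables 48 and 50 are the two-arm safety summaries.

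**The case against.** The strongest reply is that little is lost. Hemoglobin is graded in Tables 15, 47 and 48, which says more about anemia than a count of low RBC values would. White cells, neutrophils, lymphocytes and platelets are graded as well. Hyponatremia and the other low electrolytes have their own rows. SAP 7.7.2 plans no between-arm test, the shells have no p-value column, and the Fisher comparison in 7.7.1 concerns overall adverse events. All of this stands, and it is why the point is minor. For low monocytes, eosinophils and basophils the documents give no particular reason for interest; they are included because the same sentence and the same fix govern them.

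A reader might go further and infer that every low value of these tests will be reported as normal. The documents do not support that. Nothing in the SAP says so, and step 3 of the working shows that such values may instead be left out. A reader might also infer that the SAP never shows low values for ungraded tests; the thyroid shells show otherwise.

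It can also be said that a hemoglobin threshold is not a statement about red cell count. That is fair. The step from admitted anemia to expected low RBC is an assumption, and the documents give no RBC distribution.

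**Conclusion.** The point holds as a gap between rule, shells and data. Measured low values of RBC, chloride, monocytes, eosinophils and basophils have no row and would be either counted as Normal or not shown, and the thyroid shells contradict the same sentence by omitting high values. The number of patients affected cannot be derived from the documents. The size is small: these are descriptive rows, graded hemoglobin and sodium partly cover RBC and chloride, and no endpoint, test or conclusion depends on them. The conclusion rests on reading the shells as the intended output and on the assumption that low RBC counts will occur in a population admitted with hemoglobin down to 90 g/L.

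**What to change.** - In SAP 7.7.2, replace the two categories with three (below lower limit, normal, above upper limit) for ungraded tests where both directions are meaningful, and name LDH and CEA as two-category exceptions.
- Add a below-lower-limit row for RBC, monocytes, eosinophils and basophils in Tables 15, 47 and 48, and for chloride in Tables 16, 49 and 50.
- Add an above-upper-limit row for the thyroid tests in Tables 17, 51 and 52, so that rule and shells agree.
- Because the post-baseline tables take the worst result per patient, state that a patient with both a low and a high value counts in both rows, as the separate hyper- and hypo- rows already allow for sodium.
- In the same edit, remove RBC, chloride and the other ungraded tests from the lists promising a worst CTC grade, and correct the Table 15 footnote defining High, which names both an upper and a lower limit.

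The cost is one rewritten sentence and a few table rows. The tests are already scheduled in both arms, so nothing new is asked of patients. The one dependency is that lower limits of normal must be available for the five tests; the documents do not say whether they are captured, and this should be confirmed before the shells are changed.
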